 - Renal function indicators: blood urea nitrogen (BUN), serum creatinine, and estimated Glomerular filtration rate (eGFR)
 - Electrolytes: sodium, potassium, chloride, total calcium and bicarbonate
- [8] Coagulation: Prothrombin time (PT) and international normalized ratio (INR)
- [9] ONLY performed on women of childbearing potential. # ONLY performed when early termination occurs before the completion of Visit 3.
- [10] Urinalysis: color, appearance, specific gravity, pH, protein, glucose, occult blood, ketones, leukocyte esterase, nitrite, bilirubin, urobilinogen, and microscopic examination of urine sediment.

Evaluated biomarkers will include: [REDACTED]

[REDACTED]

[REDACTED]

[REDACTED]

- [12] Swabs will be used for rapid diagnostic test, RT-PCR for presence of viral RNA (qualitative tests), Ct value and viral load:
 - At Screening, perform a rapid diagnostic test for SARS-CoV-2 or influenza virus infection using a nasopharyngeal specimen.
 - Nasopharyngeal swab for RT-PCR should be collected on Day 1 and Day 7.

ONLY performed when early termination occurs before the completion of Visit 3.

- [13] Baseline assessments (on Day 1) should be conducted prior to administering the first dose of CX-4945 or placebo. Drug administration is twice daily for 5 consecutive days, starting on Day 1 and completing on Day 5, or on Day 6 if only one dose is administered on Day 1.
- [14] Patients will be instructed on the use of the Electronic Patient Reported Outcomes (ePRO) for all dose administrations and body temperature record [4] at Visit 2. Site staff will check the completeness of ePRO at Visit 3 and Visit 4, and if necessary, at Visit 5. Patients may record dose administration on Day 1 ~ Day 6 and body temperature on Day 1 ~ Day 7 or beyond, as needed.
- [15] Visit 1 and Visit 2 could be the same day. When Visit 1 and Visit 2 occur on the same day, the same assessments from Visit 2 can be omitted.
- [16] The results acquired from Visit 1 should serve as the baseline for the Chest X-ray and 12-lead ECG.
- [17] Adverse events, concomitant medications and hospitalization events will be recorded at an unscheduled visit (UV); other assessments will be performed at the investigator's discretion.
- [18] If the subjects have lost IPs, only one more dispensation of the investigational product is allowed per subject based on the pharmacy manual.

TABLE OF CONTENTS

SIGNATURE PAGE	2
PROTOCOL ACKNOWLEDGEMENT FORM	3
SYNOPSIS	4
SCHEDULE OF ASSESSMENTS	12

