3.2.2. Inclusion criteria

Subjects meeting all of the following criteria will be considered for enrollment into the study:

1. Not currently hospitalized
2. Males or females aged ≥ 18 years at the time of signing the informed consent form (ICF)
3. Patients diagnosed with viral pneumonia, as determined by the investigator, who exhibit any of the subsequent criteria: presence of respiratory symptoms or fever (ear temperature ≥ 38 °C, base of the tongue temperature ≥ 37.5 °C, or axillary temperature ≥ 37 °C)
4. With a pneumonia severity index (PSI) of risk class II or III
5. Oxygen saturation measured by pulse oximetry (SpO_2) $\geq 94\%$ on room air at sea level
6. Positive test for SARS-CoV-2 or influenza virus infection, confirmed by rapid diagnostic test (excluding cases where both SARS-CoV-2 and influenza virus are positive)
7. Confirmed lower respiratory tract infection by X-ray
8. At screening, subjects capable of childbearing must provide a negative serum or urine pregnancy test. These subjects must also commit to adhering to the study-specified contraceptive methods throughout the study duration

Notes: Acceptable contraceptive methods include:

- Established use of oral, injected or implanted hormonal methods of contraception
- Placement of an intrauterine device (IUD) or intrauterine system (IUS)
- Barrier methods of contraception: condom or occlusive cap (diaphragm or cervical/vault caps)

9. The participant (or legal representative) agrees and is able to adhere to study protocol-stated requirements, instructions, and restrictions in the investigator's judgement. Furthermore, the participant is capable of understanding and has signed the IRB-approved Informed Consent Form (ICF)

10. With at least two of the risk factors listed below:

Age \geq 50 years-old; cancer and a life expectancy of \geq 6 months; HIV infection; immunocompromised patient; congestive heart failure (CHF), or coronary artery disease (CAD), or cardiomyopathies; chronic kidney disease (CKD); chronic liver disease; chronic lung disease; diabetes mellitus (DM); body mass index (BMI) $> 25 \text{ kg/m}^2$; asthma; cerebrovascular disease; cystic fibrosis; dementia; or current and former smoker

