To evaluate the effect of intervention with Silmitasertib (CX-4945) in addition to SOC, compared with placebo plus SOC, on reducing viral presence	
 
• The percentage of subjects with a negative RT-PCR result for the SARS-CoV-2 (only for SARS-CoV-2 domain) or the influenza virus (only for influenza virus domain) on Day 7 FilmArray data (Negative/Positive) obtained from Protocol v.1.0 will be integrated into and considered equivalent to the results for RT-PCR.
 

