### **3 STATISTICAL CONSIDERATIONS**

#### **3.1 ANALYSIS POPULATION**

The following populations will be introduced for statistical analysis.

Analysis population	Description
Intent-to-Treat (ITT) Population	All randomized subjects who receive at least one dose of CX-4945 or placebo
Per-Protocol (PP) Population	

• The set of subjects who meet the ITT population

• Receive 80 - 120% of 10 doses of the IP during Days 1 - 6 or die before Day 6

• Not associated with any major protocol violations that have impact on efficacy evaluation

Modified Per-Protocol (mPP) Population =Evaluable subjects	

• The set of subjects who meet the ITT population

• Receive 80 - 120% of 10 doses of the IP during Days 1 - 6 or die before Day 6

• Complete the required visits by Visit 4 or die before Visit 4

• Not associated with any major protocol violations that have impact on efficacy evaluation by Visit 4

ITT population will be used as the primary analysis population for efficacy endpoints and the analysis population for baseline data, safety and exploratory endpoints. PP population will also be applied on AE analysis. PP and mPP populations will be used as the supportive analysis population for efficacy endpoints.

All analyses will be performed on actual treatment taken unless otherwise specified. For PP and mPP populations, all inclusion and exclusion criteria should be fulfilled as applied in the latest version.

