**The percentage of subjects exhibiting disease progression / health improvement in health status**

NIAID score and changes in NIAID score will be tabulated descriptively by visit. For protocol version 1.0, 6-Point Ordinal Scale collected for subjects of Influenza Virus domain will be converted to corresponding NIAID score (*refer to [Instructions and Abbreviations] of Subject Data Listings Specification for NIAID 6-point Score Conversion to 8-point Score*) and combined with NIAID score for analyses.

The percentage of subjects with increasing NIAID score (exhibiting disease progression) and with decreasing NIAID score (exhibiting health improvement) will be presented with the corresponding Clopper-Pearson exact 95% CI, and tested by using Fisher's exact test or Cochran-Mantel-Haenszel test, respectively.

**The percentage of subjects with a negative RT-PCR result for the SARS-CoV-2 (only for SARS-CoV-2 domain) or the influenza virus (only for influenza virus domain) on Day 7**

The percentage of subjects with RT-PCR negative results will be tested between treatments by using Chi-square test or Fisher's Exact test.

FilmArray data (Negative/Positive) obtained from Protocol v.1.0 will be integrated into and considered equivalent to the results for RT-PCR.

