**Statistical Analysis Plan**  
CX-4945 for Community-Acquired Pneumonia

---

For subgroup of subjects with baseline [REDACTED] levels exceed ULN, Clinical Relevance analyses will be performed additionally, and the percentage of subjects achieving normalized [REDACTED] levels on Day 7 will be presented with corresponding Clopper-Pearson exact 95% CI, and tested by using Fisher's exact test or Cochran-Mantel-Haenszel test.

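### The Day 7 RT-PCR negativity endpoint has no Day 1-positive denominator, so any subject negative on both days dilutes the treatment comparison

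*SAP*

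**What the plan says.** The endpoint is the percentage of subjects with a negative RT-PCR for their domain virus on Day 7. SAP Section 1 places it under the objective of evaluating CX-4945 plus SOC, compared with placebo "plus SOC, on reducing viral presence". SAP 3.2.4 gives the analysis in one sentence: "The percentage of subjects with RT-PCR negative results will be tested between treatments", with a chi-square or Fisher's exact test. Protocol 7.7.2 has the same rule. Version 1.0 FilmArray results are treated as equivalent to RT-PCR.

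The virological entry criterion (Protocol 3.2.2, criterion 6) is "Positive test for SARS-CoV-2 or influenza virus infection, confirmed by rapid diagnostic test". RT-PCR comes later. Footnote 12 of the Schedule of Assessments says "Nasopharyngeal swab for RT-PCR should be collected on Day 1 and Day 7", and footnote 13 puts Day 1 baseline assessments before the first dose.

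SAP 3.1 says "ITT population will be used as the primary analysis population for efficacy endpoints". ITT means randomized and dosed. PP and mPP add compliance, deviation and eligibility conditions (mPP also visit completion), but no RT-PCR condition.

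Two other endpoints are conditioned on baseline. Fever resolution (SAP 3.2.4) is analysed in subjects febrile at baseline. Normalization of the inflammatory marker (SAP 3.2.6) is analysed in a subset introduced by "For subgroup of subjects with baseline", namely those above the upper limit of normal.

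**The concern.** A subject with a positive rapid test at screening can have a negative RT-PCR on Day 1. Screening may fall up to two days earlier, a different assay is used, and nothing requires Day 1 RT-PCR positivity. If that subject is negative again on Day 7, the result counts in the favourable category although there was no detectable virus to reduce after dosing began.

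Such subjects raise the percentage in both arms, pull the arms together, and add noise when they fall unevenly between arms. This matters most in influenza. Viral load and Ct are measured only in the SARS-CoV-2 domain (Protocol 5.2.4.4), so Day 7 negativity is the only virological measure in the influenza domain and no baseline-adjusted analysis stands beside it.

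**Working it through.** The documents give no figure for this endpoint, so there is none to reproduce.

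**Inputs from the documents.** 44 subjects randomized (SAP 3.4.1) at 1:1 (SAP 2.2), so about 22 per arm pooled; the actual split is not given. Two-sided 0.05 (SAP 3.2.2). Chi-square or Fisher's exact test (SAP 3.2.4).

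**Assumptions.** q is the share RT-PCR negative on Day 1, the same in both arms in expectation and still negative on Day 7. p is the Day 7 negative rate among Day 1 positives. No Day 7 swab is missing. Neither q nor p is in the documents.

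**Dilution.** The all-subject rate is q + (1 − q)p, so the difference is (1 − q)(p_active − p_control).

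**Chi-square-type z.** z = difference / √[2·p̄(1 − p̄)/n], where p̄ is the mean of the two rates. n is 22 for all subjects and 22(1 − q) for the restricted analysis. With p = 40% versus 70%:

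| q | All-subject rates | Difference | z, all | n per arm, restricted | z, restricted |
|---|---|---|---|---|---|
| 0 | 40% / 70% | 30 | 2.00 | 22 | 2.00 |
| 10% | 46% / 73% | 27 | 1.82 | 19.8 | 1.90 |
| 20% | 52% / 76% | 24 | 1.66 | 17.6 | 1.79 |

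For example, at q = 10% in all subjects, p̄ = 0.595 and z = 0.27/√(2 × 0.595 × 0.405/22) = 0.27/0.148 = 1.82.

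**Exact Fisher power**, 22 per arm, p = 30% versus 60%, with the restricted analysis averaged over the binomial number of Day 1 positives:

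| q | Difference, all | Power, all | Power, restricted (30 points) |
|---|---|---|---|
| 0 | 30 | 40% | 40% |
| 5% | 28.5 | 36% | 40% |
| 10% | 27 | 32% | 39% |
| 20% | 24 | 25% | 37% |
| 30% | 21 | 20% | 30% |

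Restriction never loses power in this range, despite the smaller denominator.

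**Negatives without reduction.** Their share of Day 7 negatives is q/[q + (1 − q)p]. At q = 10% and p = 30% versus 60%, this is 0.10/0.37 = 27% in control and 0.10/0.64 = 16% in active.

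**Chance imbalance.** With 22 per arm, the probability that Day 1 negatives differ by three or more subjects is 8%, 20%, 34% and 41% at q = 5%, 10%, 20% and 30%. Three extra Day 1 negatives in a control arm with p = 40% raise its expected rate by (3/22)(1 − 0.40) = 8.2 points.

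**Type I error.** With p = 40% in both arms, Fisher's test in all subjects rejects in 2.2% to 2.3% of trials at every q examined. It is not inflated.

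**The case against.** The best defence is that this is a status endpoint. The plan asks whether the Day 7 RT-PCR is negative and never speaks of clearance, so a Day 7 negative is counted as defined. Randomization keeps the all-ITT comparison valid under the null, and any dilution is conservative. Both points stand. A reader might infer that the rule favours the drug or raises the false-positive rate, but the type I error calculation shows otherwise.

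Second, fever and a raised marker are not entry requirements, whereas a positive viral test is, so entry already supplies a virological baseline condition. Subjects who entered on FilmArray under version 1.0 were positive at screening by an assay the SAP accepts as equivalent, and for them the issue largely disappears. This limits the concern. It does not remove it for subjects who entered on a rapid test, and the documents give neither group's size.

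Third, the size is assumed, and no Day 1-negative subject is documented. A reader using an unpooled z for 40% versus 70% would get 1.99 restricted against 1.90 for all subjects at q = 10%, and might conclude that the denominator decides significance. That crossing of 1.96 comes from the unpooled formula. On the pooled variance behind the planned chi-square test, neither analysis reaches 1.96 at q = 10% or 20%.

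Fourth, the SARS-CoV-2 domain already has viral load and Ct change, analysed by ANCOVA with the baseline value in the model (SAP 3.3.1). That is a partial answer, since influenza has no equivalent.

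**Conclusion.** The point holds as a modest, optional improvement. The analysis text has no Day 1-positive condition, and the objective it serves is a reduction. The consequence is a difference diluted by (1 − q), extra sensitivity to chance imbalance, and a percentage that is easily misread as viral reduction. The planned test is not invalid, and the trial is explicitly not sized on power.

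On the assumed rates, the loss is 3 points at q = 10% and 6 points at q = 20%. Exact power falls to 32% against 39%, and to 25% against 37%, so power is low either way. At q = 0 the two analyses are identical.

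That all subjects enter the denominator is inferred from the absence of a restriction, together with the explicit restrictions on two other endpoints. The mock-up tables are separate documents (SAP 3.6) and were not available. If they already restrict the denominator, the SAP text should say so.

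**What to change.** In SAP 3.2.4, add a sentence such as: *Day 7 negativity will be tested among ITT subjects with a positive Day 1 RT-PCR (or positive baseline FilmArray under protocol version 1.0) for their domain virus, by domain and pooled with a Cochran-Mantel-Haenszel test stratified by domain.* Keep the all-ITT percentage as a supportive analysis, and report the number of Day 1 negatives by arm and domain so that readers can see q.

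The Day 1 swab is already collected before dosing, so the subset is defined before treatment and the restriction preserves the randomized comparison. The stratified test uses a randomization stratum and is already a general option for pooled comparisons in SAP 3.2.2. The cost is a slightly smaller denominator and one additional table. The change should be made before unblinding; if made later, it should be labelled post hoc.

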**Change from baseline in viral load in nasal secretions by RT-PCR (only for SARS-CoV-2 domain)**

The viral load and changes in viral load in nasal secretions by RT-PCR will be summarized descriptively by visit. The change from baseline will be analyzed by using ANCOVA.

**Change from baseline in Ct values (only for SARS-CoV-2 domain)**

The Ct values and changes in Ct values will be summarized descriptively by visit. The change from baseline will be analyzed by ANCOVA.

**3.2.5 SAFETY ANALYSES**

**Treatment-emergent Adverse Events (TEAEs)**

**Statistical Analysis Plan**  
CX-4945 for Community-Acquired Pneumonia

---

AEs occurring during the study will be coded using the most recent version of Medical Dictionary for Regulatory Activities (MedDRA). The adverse events will then be grouped by MedDRA preferred terms into frequency tables according to system organ class. All reported adverse events, as well as adverse events judged by the investigator as at least possibly related to IP, will be summarized according to system organ class and preferred term within system organ class. When an adverse event occurs more than once for a subject, the maximal severity to the IP will be counted.

An overview of TEAEs will be presented with number and percentage. Separate summaries will be produced for the following categories, such as TEAEs, SAEs, Treatment-Related TEAEs, TEAEs resulting in discontinuation of study treatment and TEAEs leading to death will be presented. All coding terms will be included in the subject data listing.

### **Physical Examination**

All physical examination findings will be listed. Physical abnormalities will be tabulated descriptively by visit.

### **Laboratory Tests**

For continuous laboratory data, the values and changes will be summarized descriptively by visit. The change from baseline will be analyzed by using ANCOVA.

For categorical laboratory data, the values and transition from baseline will be tabulated descriptively by visit. The transition from baseline will be tested by using Fisher's exact test or Cochran-Mantel-Haenszel test. Clinical relevance ("Normal", "Abnormal, non-clinical significant (NCS)" or "Abnormal, clinical significant (CS)") and its transition from baseline will be tabulated descriptively.

### **Vital Signs**

The values and changes in vital signs will be summarized descriptively by visit. The change from baseline will be analyzed by using ANCOVA.

### **ECG**

For overall interpretation of ECG, the by visit result and its transition from baseline will be tabulated descriptively by visit. The transition from baseline will be tested by using Fisher's exact test or Cochran-Mantel-Haenszel test.

For continuous ECG data, the values and changes will be summarized descriptively by visit. The change from baseline will be analyzed by using ANCOVA.

### **3.2.6 EXPLORATORY ANALYSES**

#### **The percentage of subjects achieving normalized [REDACTED] levels on Day 7**

Clinical Relevance ("Normal", "Abnormal, non-clinical significant (NCS)" or "Abnormal, clinical significant (CS)") of [REDACTED] and its transition from baseline will be tabulated descriptively by visit.

**Statistical Analysis Plan**  
CX-4945 for Community-Acquired Pneumonia

---

For subgroup of subjects with baseline [REDACTED] levels exceed ULN, Clinical Relevance analyses will be performed additionally, and the percentage of subjects achieving normalized [REDACTED] levels on Day 7 will be presented with corresponding Clopper-Pearson exact 95% CI, and tested by using Fisher's exact test or Cochran-Mantel-Haenszel test.

**Change from baseline in [REDACTED]**

The values and changes in these tests will be summarized descriptively by visit. The change from baseline will be analyzed by using ANCOVA.

**Changes from baseline in serum cytokine levels: Cytokines to be quantified; [REDACTED]**

The values and changes in these tests will be summarized descriptively by visit. The change from baseline will be analyzed by using ANCOVA.

### **3.2.7 BASELINE STATISTICS**

Demographics and baseline characteristics including medical history, prior and concomitant medications/therapies and treatment exposure up to Day 6 and total treatment exposure will be summarized using appropriate statistics mentioned in section 3.2.2.

### **3.2.8 PATIENT DISPOSITION**

The disposition of all patients who signed an ICF will be provided. The number of subjects screened, screen failed, randomized, received at least one treatment, completed, and discontinued during the study, as well as the reasons for all discontinuations will be summarized.

### **3.2.9 CONCOMITANT MEDICATIONS/THERAPIES/MEDICAL PROCEDURES**

All medications will be coded to matching Anatomic Therapeutic Classification (ATC) codes using the most recent version of the WHO Drug Dictionary. Percentage of taking prior medication and concomitant medications will be presented, respectively, by the highest ATC level.

All medical procedures including surgery will be coded using the most recent version of Medical Dictionary for Regulatory Activities (MedDRA). Percentage of receiving prior medical procedures and concomitant medical procedures will be presented, respectively, by the system organ class and preferred term.

All coding terms will be included in the subject data listing.

### **3.2.10 VISIT ADJUSTMENT**

For all efficacy and safety analyses, the visit (not including unscheduled visit) out of acceptable window and the Early Termination Visit (Visit 5) of early terminated subject will be reallocated to an appropriate scheduled visit according to below acceptable visit window.

Visit Name	Visit Day	Acceptable visit window
Visit 1 (Screening)	-1 ~ 1 (v1.0)	NA

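### No specified laboratory, ECG or vital-sign summary has a stated place for unscheduled values, and the SAP plans no worst-post-baseline table

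*SAP*

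**What the plan says.** **Visit rule.** SAP 3.2.10 covers all efficacy and safety analyses. It states that "the visit (not including unscheduled visit) out of acceptable window and the Early Termination Visit (Visit 5) of early terminated subject will be reallocated" to a scheduled visit. The windows are Day 4 to 10 for Visit 3, Day 11 to 20 for Visit 4 and Day 21 to 40 for Visit 5.

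**Safety summaries (SAP 3.2.5).**
- Laboratory: "For continuous laboratory data, the values and changes will be summarized descriptively by visit". Categorical laboratory results are handled the same way. For Clinical Relevance (normal, abnormal NCS, abnormal CS), the result "and its transition from baseline will be tabulated descriptively", with no mention of visit.
- Vital signs: "The values and changes in vital signs will be summarized descriptively by visit".
- ECG: "For overall interpretation of ECG, the by visit result and its transition from baseline will be tabulated descriptively by visit" and "For continuous ECG data, the values and changes will be summarized descriptively by visit".

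No worst-value, any-time, threshold or toxicity-grade summary is specified for any of the three.

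**Unscheduled visits.** Under footnote [17] of the protocol's Schedule of Assessments, adverse events, concomitant medications and hospitalization events are always recorded, and "other assessments will be performed at the investigator's discretion".

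**The concern.** A laboratory test or ECG done at the investigator's discretion between scheduled visits is likely to have been prompted by a concern, so these values carry safety information out of proportion to their number. A table built only from scheduled visits cannot show an abnormality that arises and resolves between two of them.

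The gap matters more here because treatment lasts five days and the first scheduled post-dose sample under the current protocol comes around or after the last dose. The SAP lists laboratory tests and ECG as safety endpoints separate from TEAEs, with time frames of Day 1 to Day 29 and baseline to Day 29. The specified summaries show them mainly at three post-baseline visits. A transient hepatic, renal, neutrophil or QTc change during dosing is the kind of finding that could be missed in those tables.

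**Working it through.** The plan gives no figure to reproduce. The check compares days, then traces where an unscheduled value can appear.

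**1. Scheduled sampling against dosing days.** Inputs: Day 1 assessments are pre-dose, and dosing ends on Day 5, or on Day 6 if only one dose is taken on Day 1 (Schedule of Assessments, footnote [13]). Visit 3 is Day 7 ± 1 in the current protocol and was Day 5 ± 1 under v1.0 (SAP 3.2.10).

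| Protocol version | Visit 3 days | Last dose | Visit 3 days that are dosing days | Dosing days from Day 2 with no scheduled laboratory test or ECG |
|---|---|---|---|---|
| v2.0/v3.0 | 6–8 | Day 5 | none | 2, 3, 4, 5 |
| v2.0/v3.0 | 6–8 | Day 6 | 6 | 2, 3, 4, 5 |
| v1.0 | 4–6 | Day 5 | 4, 5 | 2, 3 |
| v1.0 | 4–6 | Day 6 | 4, 5, 6 | 2, 3 |

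Under v2.0/v3.0, a laboratory or ECG value on Days 2 to 5 can come only from an unscheduled or an early-termination visit.

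**2. SAP windows.** The windows 4–10, 11–20 and 21–40 cover every day from 2 to 40 except Days 2 and 3. An early-termination visit on Days 4 to 6 goes to Visit 3 and is tabulated. One on Day 2 or 3 has no visit to go to.

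**3. Where an unscheduled value can appear.**
- By-visit laboratory, ECG and vital-sign tables: no stated route, because 3.2.10 does not allocate the visit.
- Laboratory Clinical Relevance transitions: unclear. The sentence omits any reference to visit but does not say which post-baseline value is used.
- Subject listings: yes (SAP 3.2.2 and 3.3.11).
- TEAE tables: yes, if the investigator reports the finding as an adverse event. Those tables are organized by system organ class and preferred term, not by visit.

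**4. Size.** SAP 3.4.1 gives 44 randomized. Assuming an even split over both domains, 44/2 = 22 per arm. Take a subject whose ECG interpretation is normal at baseline, abnormal at an unscheduled visit on Day 4, and normal at Visits 3, 4 and 5. The by-visit transition tables count 0/22 = 0%. A worst-value table counts 1/22 = 4.5%, and two such subjects in one arm would give 2/22 = 9.1%. The true number is not in the documents and may be zero.

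**The case against.** The strongest reply is that adverse-event reporting already covers this. Protocol 6.1 and 6.1.1 include abnormal laboratory findings in the AE and TEAE definitions, and 6.3 asks investigators to grade laboratory abnormalities. The investigator also judges clinical significance for laboratory results and ECGs, and AEs are recorded at every unscheduled visit. A marked abnormality, such as a new Grade 3 ALT, would be expected in the TEAE tables. A reader might infer that unscheduled values reach no safety table at all, and the documents do not support that.

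The cover is still incomplete. It depends on the investigator's judgement, and 6.1 excludes non-serious events of expected disease progression. Protocol 5.2.4.2 (X-ray) and 5.2.5.2 (vital signs) tell the site to record clinically significant findings as AEs, but 5.2.5.3 (ECG) and 5.2.5.5 (laboratory) do not.

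Three further replies have force:
- The parenthesis in 3.2.10 limits reallocation. It does not say that unscheduled values are discarded, and the table shells are in a separate document. Exclusion is an inference, though a strong one, since no text says how such values would enter a by-visit table.
- Keeping symptom-driven values out of visit means is sound, and with 44 subjects the listings can be read in full. That justifies the by-visit tables but does not supply a per-arm comparison of worst values.
- Worst values depend on how often a subject was sampled, which can differ between subjects and arms. This stands, and the added tables should say so.

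**Conclusion.** The point holds in limited form. Unscheduled laboratory, ECG and vital-sign values have no stated place in any specified summary of those data, and no worst-post-baseline table makes up for it. Under v2.0/v3.0, a transient laboratory or ECG abnormality on Days 2 to 5 that has resolved by Visit 3 could show as no change in the by-visit tables. Each such subject is about 4.5% of an arm, assuming 22 per arm.

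A reader might also infer that SAP 3.2.10 removes nearly all on-treatment data. It does not. Visit 3 under v1.0, a Day 6 Visit 3 with a Day 6 dose, and early-termination visits on Days 4 to 6 are all tabulated, and body temperature is self-recorded four times daily during dosing. The number of subjects treated under v1.0 is not given. The lack of scheduled laboratory tests and ECGs on Days 2 to 5 comes from the protocol schedule, and no SAP change can create those data. Nor can it be said that the safety results are biased towards no signal, because the number of unscheduled values is unknown. The change is worth making because laboratory and ECG results are endpoints in their own right and the data are already collected.

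**What to change.** Keep the by-visit tables. Add to SAP 3.2.5, per arm, baseline-to-worst-post-baseline transition tables that use all scheduled, early-termination and unscheduled post-dose values, for:
- laboratory Clinical Relevance, and CTCAE v5.0 grade where one is defined;
- ECG overall interpretation;
- maximum QTcF and maximum change in QTcF from baseline.

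State in 3.2.10 that unscheduled values count for these tables, and that early-termination values on Days 2 and 3, which fall in no window, count as well.

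The cost is SAP wording and a few extra tables, with no new data collection. There is a small downside: worst values reflect unequal sampling intensity between subjects. A footnote should say this, and giving the number of post-baseline values per arm beside each table would help the reader judge it.
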